HIV	Human Immunodeficiency Virus
HR	heart rate
IB	Investigator's Brochure
ICF	informed consent form
ICH	International Council for Harmonization
IND	Investigational New Drug application
IRB	Institutional Review Board
IUD	intrauterine device
MedDRA	Medical Dictionary for Regulatory Activities
PD	Pharmacodynamic
PI	Principal Investigator
PK	Pharmacokinetic
SAE	serious adverse event
SBP	systolic blood pressure
SBTI	soybean trypsin inhibitor
SOP	standard operating procedure
T2DM	Type 2 diabetes mellitus
TEAE	treatment-emergent adverse event
TSH	thyroid stimulating hormone
ULN	upper limit of normal
WCBP	woman of childbearing potential

WHO World Health Organization

1 INTRODUCTION

Diabetes mellitus is a chronic metabolic disorder that has reached epidemic proportions in the United States, affecting almost 8% of the U.S. population in 2007, and worldwide (Centers for Disease Control and Prevention, 2008). Diabetes mellitus is defined by hyperglycemia (increased concentration of glucose in the blood) caused by defective insulin secretion (type 1), resistance to insulin action (type 2), or a combination of both. Diabetes mellitus leads to an increased risk of microvascular damage (retinopathy, nephropathy and neuropathy), reduced life expectancy, increased risk of macrovascular complications (ischemic heart disease, stroke, and peripheral vascular disease), and diminished quality of life. This illness requires continuing medical care and patient self-management and education to prevent acute complications and to reduce the risk of long-term complications (American Diabetes Association, 2009).

The World Health Organization has established diagnosis criteria for type 2 diabetes mellitus (T2DM) of fasting plasma glucose greater than or equal to 126 mg/dL (7.0 mmol/L), plasma glucose greater than or equal to 200 mg/dL (11.1 mmol/L) at 2 hours following ingestion of 75 g anhydrous glucose in an oral glucose tolerance test, or random plasma glucose greater than 200 mg/dL (11.1 mmol/L) in a person with symptoms of diabetes (World Health Organization, 2006). The treatment goal for patients with this disease is long-term glycemic control (over both fasting and non-fasting blood glucose levels), which has been demonstrated in both type 1 and type 2 patients to reduce the morbidities associated with uncontrolled glycemic levels (Diabetes Control and Complications Trial Research Group, 1993; Cleary et al., 2006; UK Prospective Diabetes Study Group, 1998a & 1998b). Typical options for glycemic control in patients with T2DM include lifestyle management (diet and exercise), exogenously administered insulin, insulin plus oral drugs such as metformin or sulfonylureas, and oral drugs alone. Glycemic control is measured by patient self-monitoring of blood glucose (SMBG), patient self-monitoring of interstitial glucose, and periodic blood tests for measurement of hemoglobin A1C (HbA1c). HbA1c levels reflect average glycemia over several months and therefore provide a surrogate for glycemic control (U.S. Food and Drug Administration, 2008). A consensus statement written by the American Diabetes Association and the European Association for the Study of Diabetes targets an HbA1c level of <7% as an objective for nonpregnant adults, who do not have complicating factors, for the prevention of micro- and macrovascular disease (Nathan et al., 2009).

In addition to lifestyle modification through diet and exercise, a number of treatments are available to treat hyperglycemia in diabetic patients. The choice of antihyperglycemic agents is made between physicians and patients based upon the agents' effectiveness in lowering glucose, other effects that can reduce long-term complications, safety, tolerability, ease of use, and expense. For example, metformin is widely prescribed as an initial therapy to improve glycemic control in patients with T2DM. It decreases hepatic glucose output and lowers fasting glycemia, thereby reducing HbA1c levels. It is generally well-tolerated, with possible gastrointestinal adverse events and low incidence of hypoglycemia, but is contraindicated in patients with renal dysfunction. Sulfonylureas lower glycemia by enhancing insulin secretion, and are effective in lowering HbA1c levels. Possible adverse events associated with this class of drugs include hypoglycemia (more frequent in elderly patients) and weight gain. Other drugs such as thiazolidinediones (TZDs), Glucagon-Like Peptide 1 (GLP-1) analogue, α -glucosidase inhibitors, glinides, and pramlintide are commercially available in the U.S., but are considered less well-

validated with respect to established use, efficacy, and cost-effectiveness for achieving target glycemic goals than lifestyle management, metformin, and sulfonylureas (Nathan et al., 2009).

Subcutaneously administered insulin is highly effective at lowering glycemia and helping patients achieve target HbA1c levels. Insulin has no overall dose limit with respect to safety and provides an improved lipid profile. However, subcutaneously administered insulin requires daily injections and blood glucose monitoring, and is associated with weight gain and an increased risk of hypoglycemia. Insulin is available as formulations with different pharmacokinetic (PK) and pharmacodynamic (PD) profiles (e.g, rapid, regular, intermediate, or long acting, or mixtures of these). These different formulations are used (Nathan et al., 2006) to tailor appropriate insulin regimens on a per patient basis.

Oramed Ltd. is developing a proprietary oral formulation of recombinant human insulin (ORMD-0801). Oramed, located in Jerusalem, Israel, was established in 2006 and the company's proprietary platform technology is based on over 25 years of medical research at the Hadassah University Medical Center in Jerusalem, Israel. In addition to ORMD-0801, which is the most advanced product in Oramed's pipeline, the pipeline also includes an insulin suppository, and a GLP-1 analogue.

ORMD-0801 is based on Oramed's platform technology for the oral delivery of polypeptides, which includes a proprietary formulation of excipients to facilitate oral uptake by hindering proteolysis in the small intestine and facilitating translocation of peptides across the gut epithelial lining, and into the systemic circulation. The formulation for ORMD-0801 includes aprotinin and soybean trypsin inhibitor (SBTI) to hinder proteolysis, and disodium ethylenediaminetetraacetic acid (EDTA) to facilitate translocation. The fish oil provides omega-3 fatty acids. The gelucire is used for its emulsifying properties. The enteric-coated capsules are designed to disintegrate in a pH-dependent manner in the small intestine. The initial indication for ORMD-0801 is to reduce fasting blood glucose in adult subjects with type 2 diabetes mellitus with the objective of controlling the overall average glycemic level.

The potential advantage of oral insulin in the treatment of elevated fasting blood glucose as compared to subcutaneously-administered insulin lies in its delivery to the hepatic portal vein. Orally-administered insulin, once transported across the gut wall, is ferried to the hepatic portal vein, mimicking the natural route of endogenous pancreatic insulin and delivering the insulin directly to the intended site of action. In contrast, subcutaneously-administered insulin reaches the liver through the systemic circulation thereby requiring higher systemic levels of insulin in order to achieve the same effect. Thus, oral insulin administration is expected to avoid systemic hyperinsulinemia and provide a markedly reduced risk of hypoglycemia. The PK/PD profile of ORMD-0801 is well-suited to the control of both fasting blood glucose and subsequent pre-meal blood glucose levels due to the delayed onset of glucose lowering activity. Therefore, Oramed is pursuing the oral administration of ORMD-0801 at bed time and one or two other times during the day for the improvement of glycemic control in adult subjects with type 2 diabetes mellitus.

Oramed has completed five Phase 1 safety studies of various formulations of ORMD-0801 in healthy human volunteers. Four Phase 2 studies have been completed, two in patients with type 2 diabetes, and two in patients with type 1 diabetes. These Phase 2 studies investigated different formulations, the effect of meals at different times following ORMD-0801 administration, and the effect of ORMD-0801 on glucose as measured by continuous glucose monitoring over a ten day treatment period with three doses per day prior to meals. Notably, one Phase 2 study

assessed the safety and effectiveness on fasting blood glucose of repeat bed time administration of ORMD-0801 in patients with type 2 diabetes over a period of 6 weeks. A Phase 1/2 dose-response study was also conducted. These studies demonstrated that the drug product is well-tolerated and can effectively reduce plasma glucose and C-peptide levels. There were no significant safety observations and no serious adverse reactions were reported for the completed studies, although there were two self-reported events of hypoglycemia in the six-week, Phase 2 study.

Oramed intends to continue with clinical development of ORMD-0801 under a U.S. IND application.

2 STUDY OBJECTIVES

2.1 Primary Objectives

- To compare pre-treatment (Day 3) to end of treatment (Day 8) 24-hour CGM glucose for single and multiple doses of ORMD-0801 vs placebo.
- To evaluate safety parameters for single and multiple doses of ORMD-0801 vs placebo.

2.2 Secondary Objectives

- To compare pre-treatment (Day 3) to end of treatment (Day 8) mean daytime CGM glucose for single and multiple doses of ORMD-0801 vs placebo.
- To compare pre-treatment (Day 3) to end of treatment (Day 8) mean nighttime CGM glucose for single and multiple doses of ORMD-0801 vs placebo.
- To compare pre-treatment (Day 3) to post-treatment washout (Day 9) 24-hour CGM glucose for single and multiple doses of ORMD-0801 vs placebo.
- To compare post-prandial glucose measurements for single and multiple doses of ORMD-0801 vs placebo.
- To compare pre-treatment (Day 3) to end of treatment (Day 8) insulin pharmacokinetics (PK) for single and multiple doses of ORMD-0801 vs placebo.
- To compare pre-treatment (Day 3) to end of treatment (Day 8) C-peptide pharmacodynamics (PD) for single and multiple doses of ORMD-0801 vs placebo.
- To compare defined events of hypoglycemia for single and multiple doses of ORMD-0801 vs placebo.

3 INVESTIGATIONAL PLAN

3.1 Overall Study Design and Plan

This study will enroll approximately 30 adult subjects with T2DM from age 20 to 75 inclusive. Following a 7-10 day Screening period, eligible subjects will enter a 3-day single-blind placebo run-in. On Day 4, each subject will be randomized to a treatment sequence that will include three treatment assignments for each of three treatment Periods according to the randomization scheme. All subjects will receive placebo plus two of the following: ORMD-0801 460 IU **qd**, ORMD-0801 **bid**, or ORMD-0801 **tid**. Subjects will receive the randomized treatment from Day

4 through Day 8. A 24-hour single-blind placebo washout will be done on Day 9. For all treatment Periods, pre-treatment CGM data will be collected for approximately 36 hours prior to treatment (Days 1-3). The cannula will be changed and the monitor will remain in place throughout the 5-day treatment period (Days 4-8) and for an additional 24 hours post-treatment (Day 9). Blood samples for PD analysis will be taken pre-treatment (Day 3) and at end of treatment (Day 8) to check for concentrations of insulin and C-peptide in the blood. In addition, adverse events, clinical laboratory values, vital signs, and electrocardiograms (ECGs) will be evaluated periodically for safety. Subjects will be discharged on the morning of Day 10. Each treatment Period will be separated by a 2-week washout. A final follow-up visit will be performed 1 week after the end of the third treatment period.

3.2 Screening (7 to 10 Days prior to Visit 2)

At the Screening Visit, potential subjects will be given a detailed oral presentation describing the nature, purpose, risks, and requirements of the study and will also receive detailed written information (ICF). They will have adequate opportunity to ask the appropriate person of the Investigational staff (i.e., Principal Investigator or designee) presenting the study about any aspect of the study.

Once the subject is satisfied that he/she is willing to participate in the study, he/she will be asked to sign the study ICF (refer to Section 11.1.4 for further detail regarding the ICF). The Investigational Site personnel obtaining written consent from the subject will also sign the form to confirm consent has been obtained.

Once signed, the Investigator will retain the original ICF for the subject's study records and provide the subject with a signed copy. The Investigator will verify that informed consent has been obtained from each subject prior to enrollment into the study and prior to the subject undergoing any study-related procedures.

Screening activities subsequent to obtaining informed consent will be conducted and consist of the following:

- Completion of medical and social history, including tobacco, alcohol, caffeine, and drug use;
- Collection of demographic data (sex, age, race/ethnicity);
- Review of prior and current medications and supplements;
- Review inclusion and exclusion criteria;
- Physical examination;
- 12-lead ECG;
- Measurement of vital signs (height, weight, seated SBP/DPB, and heart rate);
- Perform breathalyzer;
- Collection of fasted blood and urine samples for:
 - Clinical safety labs, including hematology, serum chemistry (with HbA1c, C-peptide,

and TSH), and urinalysis (see Section 6.3.5 for list of tests);

- Urine drug screen;
- Serum pregnancy test (WCBP only);
- Serum FSH (to test for women in early menopause);

For subjects who meet eligibility criteria based on the Screening assessments, instruct as follows:

- Use adequate contraceptive methods (see Section 4.1) for the duration of the study (Screening through Follow-Up Visit 3);
- Keep the use of concomitant medications at a minimum during the study, if possible, and avoid prohibited medications as defined in Section 5.7;
- Maintain their usual dietary habits for the periods of the study where they will not be housed in the CRU and avoid drastic changes, such as a conversion to a vegetarian diet;
- Refrain from any unusual or unaccustomed vigorous exercise during the course of the study;
- Refrain from excessive alcohol use or binge drinking during the study, and not to drink alcohol from 72 hours prior to admission to the CRU (Visit 2/Day 1) thru discharge from the CRU;
- Refrain from excessive caffeine use (i.e., more than five cups of caffeinated beverages per day) during the course of the study;

3.2.1 Screen Failure

A screen failure is defined as a subject who has signed the ICF, does not meet all the entry criteria outlined in Section 4 of this protocol (note that this includes assessments through Visit 2/Day 1), and was not randomized to receive study treatment (active or placebo).

The Investigator is responsible for keeping a record of all subjects screened for entry into the study and subsequently excluded. The reason(s) for exclusion will be recorded in the source documents and on the Screening log.

3.3 Visit 2 (Treatment Periods 1, 2, and 3)

3.3.1 Period 1

Subjects will report to the CRU on the morning of Day 1.

3.3.1.1 Day 1

- Review of medical history;
- Review of medications and supplements;
- Measurement of vital signs (weight, seated SBP/DPB, and heart rate);

- Provide the first dose of single-blind placebo at least 45 minutes prior to breakfast;
- Provide breakfast;
- Subjects will be fitted with the continuous glucose monitoring (CGM) device and data recording will begin;
- Provide 4 doses (8 capsules) of single-blind placebo and instruct subjects to take one dose at least 45 minutes before lunch, one dose at bedtime, one dose at least 45 minutes before breakfast on Day 2, and one dose at least 45 minutes before lunch on Day 2.
- Adverse events will be monitored and recorded.
- Subjects will be instructed to return to the CRU at approximately 5pm (± 30 minutes) on Day 2.

3.3.1.2 Day 2

- Admission to the CRU at approximately 5pm (± 30 minutes);
- Review of medications and supplements;
- Measurement of vital signs (weight, seated SBP/DPB, heart rate, and temperature);
- Perform breathalyzer;
- Collect a urine sample for:
 - Drug screen;
 - Pregnancy testing (WCBP only)
- Provide a standardized diabetic meal at approximately 7pm (± 60 minutes). Standardized meals will continue throughout the remainder of the study Period.
- Provide a dose of single-blind placebo at approximately 10pm (± 60 minutes).
- Continue CGM monitoring;
- Adverse events will be monitored and recorded.

3.3.1.3 Day 3

- Review of medications and supplements;
- Measurement of vital signs (weight, seated SBP/DPB, heart and rate);
- Provide a dose of single-blind placebo at approximately 7am (± 60 minutes);
- Provide breakfast no sooner than 45 minutes after the morning dose;
- Provide a dose of single-blind placebo at approximately 1pm (± 60 minutes), at least 45 minutes prior to lunch;
- Provide lunch no sooner than 45 minutes after the afternoon dose;

- Provide dinner at approximately 7pm (\pm 60 minutes);
- Provide a dose of single-blind placebo at approximately 10pm (\pm 60 minutes);
- Collect a blood sample according to schedule (per randomization scheme, either morning, afternoon, or evening) prior to the specified dose of placebo for:
 - Pre-dose PD analysis
 - Serum chemistry
- Collect scheduled (per randomization scheme) postdose PD blood draws every 30 minutes (\pm 5 minutes) until 5 hours has elapsed;
- Replace the CGM cannula at approximately 7pm (\pm 60 minutes), such that it does not interfere with any post-dose PD blood draws;
- Adverse events will be monitored and recorded.

3.3.1.4 Day 4

- Review of medications and supplements;
- Measurement of vital signs (weight, seated SBP/DPB, and heart rate);
- Randomization
- Provide a dose of study treatment or placebo at approximately 7am (\pm 60 minutes);
- Provide breakfast no sooner than 45 minutes after the morning dose;
- Provide a dose of study treatment or placebo at approximately 1pm (\pm 60 minutes), at least 45 minutes prior to lunch;
- Provide lunch no sooner than 45 minutes after the afternoon dose;
- Provide dinner at approximately 7pm (\pm 60 minutes);
- Provide a dose of study treatment or placebo at approximately 10pm (\pm 60 minutes);
- Continue CGM monitoring;
- Adverse events will be monitored and recorded.

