3.6 Schedule of Events

Table 1 below describes the daily schedule of events from Screening Visit 1 through Follow-Up Visit 3.

Table 1: Daily Schedule of Events from Screening Through Follow-Up Visit

Visit	Screening Visit 1	Treatment Visit 2 Periods 1, 2, and 3										Follow-Up Visit 3	EW		
		Study Day	Day -7 to -10	1	2	3	4	5	6	7	8			9	10
Informed Consent	X														
Medical History	X	X													
Demographics	X														
Concomitant Medications	X	X	X	X	X	X	X	X	X	X	X	X	X	X	X
Inclusion/Exclusion Criteria	X														
Physical Exam	X												X	X	
ECG	X														
Vital Signs ¹	X	X	X	X	X	X	X	X	X	X	X	X	X	X	
Hematology/Chemistry/Urinalysis ²	X ²			X ²						X ²			X ²	X ²	
Urine Drug Screen	X		X												
Breathalyzer	X		X												
Serum Pregnancy Test ³	X														
Urine Pregnancy Test ³			X												
Placebo Administration ⁴		X	X	X							X				
CGM Monitoring ⁵		X	X	X	X	X	X	X	X	X	X				
CRU Admission			X												
Standardized Diabetic Meals ⁶		X	X	X	X	X	X	X	X	X	X				
Pharmacodynamic Samples ⁷				X					X						
Remove CGM and Download Data											X				
Randomization/Crossover ⁸					X										
Treatment Administration ⁹					X	X	X	X	X						
CRU Discharge											X				
Adverse Events		X	X	X	X	X	X	X	X	X	X	X	X	X	
Study Disposition												X	X		

- ¹Vital signs include height, weight, heart rate, systolic BP, and diastolic BP. Height will be measured at Screening only. Temperature will be measured at Visit 2/Day 2 only, prior to admission.
- ²Screening labs will include standard hematology/chemistry/urinalysis, plus HbA_{1c}, C-peptide, and TSH. FSH will also be performed for women who are pre-menopausal. On Visit 2 Days 3 and 8, chemistry analysis will be performed without hematology or urinalysis. Visit 3 and EW labs will include standard hematology/chemistry/urinalysis.
- ³Pregnancy tests will be performed for women of childbearing potential only.
- ⁴A single dose of placebo will be administered on the morning of Day 1. Subjects will be dispensed the next 4 doses (8 capsules) with dosing instructions. On Day 3 and Day 9, doses will be administered at approximately 7am (±60 minutes), 1pm (±60 minutes), and 10pm (±60 minutes).
- ⁵The CGM monitor will be fitted on Day 1, the cannula will be changed on Day 3 at approximately 7pm (±60 minutes), and the monitor will continue recording measurements until the morning of Day 10.

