5.2 Randomization

This is a single center, randomized, double-blind, 3-way crossover study. Approximately 30 eligible subjects will be randomized to placebo and 2 of the 3 possible dose groups: ORMD-0801 460 IU qd (in the evening), ORMD-0801 460 IU bid (in the morning and evening) and ORMD-0801 460 IU tid (morning, afternoon, and evening).

In order to estimate the morning, afternoon, and evening PD effect, each subject will have one period in which the PD blood samples are drawn in the morning, one period in which the PD blood samples are drawn in the afternoon and one period in which the PD blood samples are drawn in the evening. When the subject is on active therapy, the PD blood samples will be drawn after an active therapy dose (not after the placebo dummy). Thus, if the subject is taking ORMD-0801 460 IU qd, the PD blood samples will be drawn in the evening. If the subject is taking ORMD-0801 460 IU bid, the PD blood samples will be drawn in the morning or evening. If the subject is taking ORMD-0801 460 IU tid or placebo, the PD blood samples will be drawn in the morning, afternoon, or evening.

Integrium, LLC will generate and implement the randomization procedures for this trial. A computer-generated randomization schedule will be used for assigning treatment (active or placebo). The Investigational Site pharmacist will follow this randomization schedule to dispense the appropriate study treatment.

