5.8 Dietary Restrictions

Subjects will fast overnight for at least 8 hours prior to the clinical safety labs at Screening.

Subjects should not take any food for at least 45 minutes or more prior to scheduled ORMD-0801 (or placebo) dosing as described in the study design. All subjects will be provided with a standardized diabetic breakfast on Day 1, then continuing from dinner on Day 2 through breakfast on Day 10. Standardized snacks will be provided between breakfast and lunch, between lunch and dinner, and between dinner and bedtime.

Excessive caffeine use (i.e., more than five cups of caffeinated beverages per day) will not be allowed from Screening through the Follow-Up Visit 3. Excessive alcohol use or binge drinking will be discouraged during the study, and alcohol will be prohibited 72 hours prior to admission to the CRU (Visit 2/Period 1, 2, and 3/Day 1) and throughout the domiciled period (i.e., through the morning assessments on Day 10).

Subjects will also be asked to refrain from any unusual or unaccustomed vigorous exercise during the course of the study.

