8.4.3 Laboratory Evaluations

Individual clinical safety lab (hematology, serum chemistry, and urinalysis) values will be listed by visit and summarized using descriptive statistics as appropriate (i.e., mean, median, range, and standard deviation for continuous data and frequency for categorical data). Individual change from baseline (Screening) in laboratory values will be calculated and summarized descriptively. Shift tables from baseline (Visit 2/Day 1) to postdose (Visit 3) will also be produced for the laboratory assessments based on the categories of Low, Normal, and High. A clinically significant change from baseline (Screening) will be recorded as an AE if deemed appropriate by the Investigator.

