3.1. Data Listings Table of Contents

The following post-text listings will be generated.

16.1.7	Randomization Schedule
16.2.1	Subject Completion/Discontinuation
16.2.2	Protocol Deviations
16.2.3	Population Status
16.2.4.1	Demographics and Baseline Characteristics
16.2.4.2.1	Substance Use – Alcohol Potential
16.2.4.2.2	Substance Use – Tobacco / Nicotine Potential
16.2.4.2.3	Substance Use – Caffeine Potential
16.2.4.3	Subject Eligibility and Informed Consent
16.2.4.4	Medical History / Surgical History / Procedures
16.2.4.5	Prior and Concomitant Medications
16.2.5	Drug Accountability
16.2.6.1	Continuous Glucose Monitoring – 24-hour Mean Values
16.2.6.2	Continuous Glucose Monitoring – Daytime Mean Values
16.2.6.3	Continuous Glucose Monitoring – Nighttime Mean Values
16.2.6.4	Fasting Blood Glucose
16.2.6.5	Post-Prandial Blood Glucose – Breakfast, Lunch, and Dinner
16.2.6.6.1	Serum Insulin Levels
16.2.6.6.2	Serum Insulin Parameters
16.2.6.7.1	C-peptide Levels
16.2.6.7.2	C-peptide Parameters
16.2.7.1	Adverse Events

16.2.7.2	Hypoglycemic Events
16.2.8	Safety Laboratory Test Results
16.2.9.1	Vital Signs
16.2.9.2	Electrocardiogram Results
16.2.9.3	Physical Examination Results
16.2.9.4	Continuous Glucose Monitoring – Values Outside Observed Value Reference Ranges

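### Day 3 and Day 8 chemistry is drawn in a PD slot that depends on the regimen, yet its change is taken from a fasted Screening sample

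*Protocol*

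**What the plan says.** For Day 3 and Day 8 of every period, protocol 3.3 instructs staff as follows: "Collect a blood sample according to schedule (per randomization scheme, either morning, afternoon, or evening) prior to the specified dose of placebo for" two purposes, the pre-dose PD analysis and serum chemistry. Table 1, footnote 2, confirms what is measured: "On Visit 2 Days 3 and 8, chemistry analysis will be performed without hematology or urinalysis". The chemistry panel in 6.3.5.1 includes glucose and triglycerides.

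Protocol 5.2 sets the slot. It says "each subject will have one period in which the PD blood samples are drawn in the morning", and likewise one afternoon and one evening period. On active therapy the sample must follow an active dose, so "if the subject is taking ORMD-0801 460 IU qd, the PD blood samples will be drawn in the evening". A bid period may use morning or evening, and a tid or placebo period any slot.

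On fasting, 5.8 says only that "Subjects will fast overnight for at least 8 hours prior to the clinical safety labs at Screening". In the unit, breakfast and a snack come before the 1pm slot, and dinner and a snack before the 10pm slot.

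On analysis, protocol 8.4.3 says "Individual change from baseline (Screening) in laboratory values will be calculated and summarized descriptively". SAP 2.7.3 summarizes Screening and end-of-study results and compares changes from Screening between treatments by ANOVA. SAP 3.1 plans listing 16.2.6.4, "Fasting Blood Glucose", but no section schedules a fasting draw within a treatment period.

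**The concern.** Evaluating safety against placebo is one of the two primary objectives. For glucose and triglycerides, a change from Screening compares a sample of varying prandial state with a fasted one, and the share of fed samples depends on the regimen. A difference between regimens in this change could therefore arise with no drug effect.

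The crossover does not remove the problem. Each subject uses each slot exactly once, so no subject has active and placebo chemistry from the same time of day. For qd the imbalance is complete: every qd sample is an evening sample.

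**Working it through.** The plan gives no figure for this point, so there is none to reproduce.

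**1. How fasted is each slot?** Inputs: nominal doses at 7am, 1pm and 10pm, dinner at 7pm, breakfast no sooner than 45 minutes after the morning dose, no food for 45 minutes before a dose, and the pre-dose sample 45 to 5 minutes before dosing (protocol 3.3, 5.8, 6.5).
- Morning: a snack ending at 9:15pm and a sample at 6:15 to 6:55am give 9.0 to 9.7 h. At the window extremes (snack ending 10:15pm, sample 5:15am) it is 7.0 h.
- Afternoon: breakfast at 7:45am and a sample at 12:15 to 12:55pm give 4.5 to 5.2 h, less with the snack.
- Evening: dinner at 7pm and a sample at 9:15 to 9:55pm give 2.3 to 2.9 h, less with the snack.

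Only the morning slot is nominally fasted, and even there no fast is required.

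**2. Assignments that 5.2 permits**
- qd + bid: one (qd evening, bid morning, placebo afternoon).
- qd + tid: two (qd evening, with tid morning and placebo afternoon, or tid afternoon and placebo morning).
- bid + tid: four (bid morning, with tid and placebo sharing afternoon and evening either way; or bid evening, with tid and placebo sharing morning and afternoon either way).

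**3. Morning periods by regimen.** Assumption: 10 of the 30 subjects per active pair. The range covers all permitted assignments. The last column further assumes that they are used equally.

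| Regimen | Permitted range | Equal use |
|---|---|---|
| qd | 0/20 | 0/20 |
| bid | 10/20 to 20/20 | 10 + 10 × 2/4 = 15/20 |
| tid | 0/20 to 20/20 | 10 × 1/2 + 10 × 1/4 = 7.5/20 |
| placebo | 0/30 to 20/30 | 10 × 1/2 + 10 × 1/4 = 7.5/30 |

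Overall there are 30 × 3 × 2 = 180 draws, of which 60 are in the morning slot.

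**4. Spurious difference from placebo.** Let *m* be the morning share and *d* the excess of a non-fasting over a fasting glucose. With no drug effect, the mean change from Screening is d × (1 − m), so regimen minus placebo is d × (m_placebo − m_regimen). Assumption: d is 20 to 60 mg/dL, the same for afternoon and evening. The documents give no value.
- qd: the lowest is 0, with placebo 0/30. The highest uses placebo 20/30: 0.667 × 60 = +40 mg/dL. Equal use: 0.25 × d = +5 to +15.
- bid: the lowest uses bid 20/20 and placebo 0/30: −1 × 60 = −60. The highest uses bid 10/20 and placebo 20/30: (0.667 − 0.5) × 60 = +10. Equal use: (0.25 − 0.75) × d = −10 to −30.
- tid: the lowest uses tid 20/20 and placebo 0/30: −1 × 60 = −60. The highest uses tid 0/20 and placebo 20/30: 0.667 × 60 = +40. Equal use: (0.25 − 0.375) × d = −2.5 to −7.5.

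**5. Effect of the remedies.** The slot is set per period, so Day 3 and Day 8 share a clock time and standardized meals. In the Day 8 minus Day 3 change, *d* enters both terms and largely cancels. A pre-breakfast draw in every period would raise morning draws from 60 of 180 to 180 of 180.

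**The case against.** **Size and direction.** The slot shares depend on a randomization plan held separately (SAP 2.12), and the 20 to 60 mg/dL offset has no source in the documents. A reader might infer that the plan makes bid look 10 to 30 mg/dL better than placebo. That needs equal use of the permitted assignments, which is not documented, and a permitted scheme reverses the sign. This objection stands.

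**Which samples are analysed.** SAP 2.7.3 speaks of end of study. If that means Visit 3, its summary excludes Days 3 and 8. This stands in part. The general sentence in protocol 8.4.3 still applies Screening as baseline. Visit 3 gives one value per subject after all three periods, so a between-treatment ANOVA would need period-level values such as Day 8. Visit 3 has no stated fast either.

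**Fasting glucose.** The Introduction says "The initial indication for ORMD-0801 is to reduce fasting blood glucose in adult subjects with type 2 diabetes mellitus", and a reader might conclude that the trial fails to measure its own target. The documents do not support that. The sentence describes the development programme, and fasting glucose is not an objective of this trial, whose glucose efficacy is CGM-based. The SAP plans one listing and no fasting-glucose table. Every subject also has one morning-slot period.

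**Adverse events.** A reader might infer inflated AE counts in some regimens. Under 8.4.3 a change becomes an AE only if it is clinically significant and the investigator deems it appropriate, so this is conjecture.

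**Scope.** The regimen fixes the slot outright only for qd, and for all periods of a qd + bid subject. The argument covers glucose and triglycerides, not the whole panel.

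**Conclusion.** The concern holds for food-sensitive chemistry. It is certain that qd periods yield no fasting chemistry, that bid is never sampled in the afternoon, and that active and placebo samples within a subject always differ in time of day. Under protocol 8.4.3 the change from Screening therefore mixes prandial state with treatment, to a degree that varies by regimen.

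The size is not certain. With 10 subjects per pair and an offset of 20 to 60 mg/dL, both assumed, the spurious difference from placebo lies between 0 and +40 mg/dL for qd, −60 and +10 for bid, and −60 and +40 for tid. Its direction is not fixed for bid or tid. The lower limit of 0 for qd also needs afternoon and evening offsets to be equal.

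The CGM primary endpoint is not affected. The matter is worth correcting because safety is a primary objective and the main remedy is an analysis edit.

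**What to change.** **Analysis (protocol 8.4.3 and SAP 2.7.3).** Use the same period's Day 3 chemistry as baseline for Day 8 and compare treatments on that change. Keep Screening as baseline only for Visit 3, and require the same overnight fast there. State what end of study means. In the same edit, correct the shift-table baseline, which 8.4.3 places at Visit 2/Day 1, a day with no laboratory sample in the schedule. This changes wording only and removes most of the fed/fasted mismatch. It still gives no fasting value for qd and leaves regimens sampled at different times of day.

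**Schedule (preferred addition; protocol 3.3 and Table 1, footnote 2).** Draw Day 3 and Day 8 chemistry, or at least glucose and triglycerides, before the morning dose and breakfast in every period, with the fast written in. Leave the PD sample in its slot. This also fills listing 16.2.6.4 for every regimen. Subjects are already in the unit on both mornings. The cost is one short extra draw on each of Days 3 and 8 in periods with an afternoon or evening slot.
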